- 1) On the first session, participants will receive a brief standardized psychoeducation module, presented via a 15-minute video recording. This video will also explain the intervention, its rationale, and the procedure.
- 2) Participants will have 5 minutes to plan and outline a speech based on a provided topic; all participants will receive the same topic and will not be allowed to use the outline during the public speaking exposure trials.
- 3) Participants will then give six speeches that are each 3 minutes long on the same topic. All the speeches will be given in the immersive 360°-video environment to a video of audience members. Between speeches participants will have a 1-minute break and will complete the subjective units of distress scale (SUDS) before and after each speech trial.
- 4) Participants will complete steps 2-3 on the second session, with a different speech topic.
- 5) Participants will complete the two intervention sessions within a single week.

Attention Guidance Condition. The experimental attention guidance condition consists of three unique components: (1) the intervention rationale will include information about the importance of visually attending to the faces of the audience; (2) in addition to being provided a speech topic, participants will be given target audience members to focus their gaze on during the speech. They will be told that they should look at and focus on the target audience member for the whole speech; (3) between speeches, the researcher will tell participants the percentage of time they were focused on the target face.

Standard Exposure Condition. Participants in the standard exposure (i.e. control) condition will complete Steps 1-5 above, but will not receive any of the attention guidance components used in the experimental condition.

VISIT 2

Intervention – Session 2 (approximately 45 minutes)

See intervention procedures described above. All procedures are the same as in session 1 with the exclusion of the psychoeducation component.

Post-treatment Assessment (approximately 20 minutes)

Immediately following the second intervention session participants will complete a series of self-report questionnaires and a behavioral approach task.

VISIT 3

1-week Follow-up Assessment (approximately 20 minutes)

One week after the post-treatment assessment participant will return to the lab and complete self-report questionnaires and a behavioral approach task, as in the post-treatment assessment.

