ONLINE FOLLOW-UP

1-month Follow-up Assessment (approximately 10 minutes)

Research Proposal

One month after the 1-week assessment, participants will receive a link to a brief survey containing self-report questionnaires.

[figure not shown]

Figure 2. Presents a diagram illustrating the study overview

Additional Follow-up

In-person Follow-up Assessment (approximately 1 hour)

During the consent process participants will have the option to opt-in to be contacted about an additional follow-up session which will consist of an assessment similar to the baseline assessment conducted during Visit 1 of this study. The primary difference is that the assessment include a speech given to a live audience while using a wearable eye tracking device. Participants will complete a separate ICD for this follow-up appointment and will receive financial compensation.

a. Location

Laboratory for the Study of Anxiety Disorders (rooms: 3.112A, 3.112B, 3.112C, 3.112D, 3.112E, 3.112F, 3.122A, 3.122B, 3.122C, 3.122D, 3.122E, 3.122F), and in the Vision, Cognition, and Action Virtual Reality lab (SEA 4.330).)

b. Resources

[name] departmental account.

c. Study Timeline

Estimated time for study recruitment is two years, plus one year for data analysis.

Table 1. Assessment Schedule

Assessment	Online Prescreen	Baseline Assessment (Visit 1)	Intervention Session 1 (Visit 1)	Intervention Session 2 (Visit 2)	Post-intervention assessment (Visit 2)	1-Week Follow-up (Visit 3)	1-month Follow-up (Online)
DEMO	X	X					
SCID-5		X					
TRT	X	X					X
C-SSRS		X					
BAT		X			X	X	
LSAS	X	X			X	X	X
PRPSA	X	X			X	X	X
SATI		X				X	X
SUDS		X	X	X	X	X	
EYE-TRACK		X	X	X	X	X	
Heart-Rate		X	X	X	X		

Note. DEMO = demographics questionnaire (age, sex, etc.); SCID-5 = Structured Clinical Interview for DSM-5 Disorders; TRT = current treatment assessment; C-SSRS Columbia Suicide Severity Rating Scale; BAT = Behavioral Approach Task to assess peak fear, which will consist of giving a three-minute speech to an audience that is different from the audience during the intervention; LSAS = Liebowitz Social Anxiety Scale; PRPSA = Personal Report of Public Speaking Anxiety; SATI = Speech Anxiety Thoughts Inventory; SUDS = subjective units of distress scale (e.g. peak fear); EYE-TRACK = Eye tracking data. Heart-Rate = Heart rate data.

5. Measures (see table 1 above for time points at which measures will be given)

Screening and other questionnaires or assessments

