Efficacy of an Attention Guidance VR Intervention for Social Anxiety Disorder

Statistical Analysis Plan

Date: 06/20/2021

Identifiers: NCT03683823 Unique Protocol ID: 2018-04-0011

Data Analysis Plan

The primary aims of this study were to 1) examine whether an attention guidance augmentation enhanced VRET compared to VRET alone and 2) test whether changes in gaze behavior following the intervention mediated the effects VRET. To test our primary hypotheses regarding the influence of the intervention on fear of public speaking (PRPSA), we conducted Bayesian multilevel models using the *brms* package version 2.15 (Bürkner, 2018). For aim 1 we examined the interaction between assessment and group predicting the outcome post-treatment and at 1-week-followup. For aim 2, we examined the indirect (i.e., mediating) effect of proportion of fixations to uninterested (socially threatening audience members) at the post-treatment assessment, on the relationship between intervention group and the post-treatment assessment of PRPSA at the 1-week-followup (see Figure 3). To facilitate interpretation of the mediation analysis, we partially standardized the model coefficients after completing the analyses using unstandardized variables following recommendations in the literature regarding indirect effect sizes when X is dichotomous (Hayes & Rockwood, 2017; Preacher & Kelley, 2011). In all models, we included average proportion of fixations to audience members during intervention sessions as a covariate to control for variation in treatment adherence. We completed the same analyses to evaluate our secondary outcome of general social anxiety symptoms measured with the LSAS. As integrity checks on the efficacy of the attention augmentation condition we tested whether there were group differences for average number of fixations on audience members during the intervention trials, as well as whether there were differences in proportion of fixations to uninterested audience members post-intervention and at 1-week follow-up.

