Priors on the effects of the intervention on proportions of fixations to audience members were not based on previously collected data because there is no literature that clearly delineates expected changes in gaze during public speaking challenges. We chose priors that reflected modest but meaningful effects, indicating changes in gaze behavior substantial enough to have potential implications for treatment outcomes as a causal mechanism. As with the other analyses, we tested several priors reflecting smaller effects as well as an uninformative prior centered on zero.

Power analysis. We did not conduct a power analysis that reflected the sample size for the current pilot study. We had initially conducted a power analysis through a simulation study prior to COVID-19, which indicated a sample size of 60 would be sufficient to detect a meaningful effect for both aims 1 and 2. However, due to COVID-19 enrollment ended before we could meet our recruitment goals. Given that research was necessarily stopped, we decided to rely on the strengths of the Bayesian approach highlighted above to investigate whether it would be worthwhile to conduct a more extensive RCT with a larger sample.

Data and syntax are available at <https://osf.io/un92m/>.

References

Bürkner, P. C. (2018). Advanced Bayesian multilevel modeling with the R package brms. *R Journal*. <https://doi.org/10.32614/rj-2018-017>

Depaoli, S., & van de Schoot, R. (2017). Improving transparency and replication in Bayesian statistics: The WAMBS-checklist. *Psychological Methods*. <https://doi.org/10.1037/met0000065>

Hayes, A. F., & Rockwood, N. J. (2017). Regression-based statistical mediation and moderation analysis in clinical research: Observations, recommendations, and implementation. *Behaviour Research and Therapy*. <https://doi.org/10.1016/j.brat.2016.11.001>

Kruschke, J. K., & Liddell, T. M. (2018). Bayesian data analysis for newcomers. *Psychonomic Bulletin and Review*. <https://doi.org/10.3758/s13423-017-1272-1>

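### Aim 2 takes its mediator after all treatment, at the same visit as post-treatment PRPSA, and plans no check on direction, so gaze that only follows fear reduction can appear as mediation

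*SAP*

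**What the plan says.** The SAP's Data Analysis Plan makes mediation the second primary aim. The mediator is "proportion of fixations to uninterested (socially threatening audience members) at the post-treatment assessment". The outcome is described by the phrase "on the relationship between intervention group and the post-treatment assessment of PRPSA at the 1-week-followup", which names two visits. It reads most naturally as PRPSA at 1 week. The SAP points to Figure 3 for the model, and that figure is not in the text available here.

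The protocol's Procedures fix the timing. For Visit 2: "Immediately following the second intervention session participants will complete a series of self-report questionnaires and a behavioral approach task". For Visit 3: "One week after the post-treatment assessment participant will return to the lab and complete self-report questionnaires and a behavioral approach task". Table 1 schedules PRPSA at prescreen, baseline, post-intervention, 1 week and 1 month. It schedules eye tracking at baseline, in both sessions, post-intervention and at 1 week.

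On covariates the SAP says: "In all models, we included average proportion of fixations to audience members during intervention sessions as a covariate". For aim 2 it states no adjustment for post-treatment PRPSA. One-week gaze appears only in an integrity check of group differences, and the sensitivity analyses described vary the priors. In explaining its gaze priors, the SAP refers to changes "substantial enough to have potential implications for treatment outcomes as a causal mechanism".

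**The concern.** When the mediator is recorded, both sessions of six speeches are over and any fear reduction produced by treatment may already be present. No study treatment falls between that visit and the 1-week visit, so 1-week PRPSA may largely carry forward a level already reached. The one-week lag puts the mediator before the outcome measurement, but not before the change it is meant to explain. A participant who has become less afraid may look more at threatening faces as a result. With post-treatment PRPSA left out of the outcome model, the gaze coefficient can absorb that carry-over.

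Aim 2 asks how the intervention works, and the SAP says the truncated pilot is to inform whether a larger trial is worthwhile. A mechanism claim whose direction is unresolved could misdirect that decision.

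**Working it through.** **The plan's own figures.** The SAP gives no mediation paths, PRPSA SD or carry-over correlation. Its one design figure, 60 participants from a simulation before COVID-19, cannot be reproduced because its inputs are not stated. The point does not rest on it. The 10-point group difference below is the SAP's prior for the augmentation. Every other value is an assumption.

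**1. Purely reverse process, no in-session covariate.** Guidance lowers post-treatment PRPSA by 10 points (SD 15). Post-treatment PRPSA drives gaze with within-arm correlation -r. One-week PRPSA carries over with coefficient 0.85. Gaze has no effect on PRPSA.
- Group to gaze: a = r × 10/15 (gaze SD units).
- Gaze to 1-week PRPSA, given group: b = -0.85 × 15 × r = -12.75r points per SD.
- False indirect effect: a × b = -8.5r². The total effect is -0.85 × 10 = -8.5 points, so the false share is r².

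| r | a | b | a × b (points) | share |
|---|---|---|---|---|
| 0.3 | 0.20 | -3.8 | -0.77 | 9% |
| 0.4 | 0.27 | -5.1 | -1.36 | 16% |
| 0.5 | 0.33 | -6.4 | -2.13 | 25% |

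A simulation with n = 1,000,000 agrees. Adding post-treatment PRPSA to the outcome model brings b to about 0.

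**2. Same process with the planned covariate.** Let guidance shift in-session gaze by s SD, and let in-session and post-treatment gaze correlate q within arm. Assume in-session gaze relates to PRPSA only through post-treatment gaze. Then a becomes r × 10/15 - s × q and b stays at -12.75r.
- s = 0: unchanged, -0.8 to -2.1 points.
- s = 0.8, q = 0.4, r = 0.5: (0.333 - 0.32) × (-6.375) = -0.1.
- s = 0.8, q = 0.8, r = 0.5: (0.333 - 0.64) × (-6.375) = +2.0.

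Over r = 0.3 to 0.5 and q = 0.4 to 0.8 with s = 0.8, the range is -0.1 to +2.0 points. The false effect vanishes or reverses sign.

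**3. Trial-sized samples.** These are least-squares stand-ins without the informative priors, with carry-over 0.8, r = 0.3 to 0.5 and 1,000 replicates per setting. In the reverse-only process, group effects on fear are 0.5 to 0.8 SD. In the last column guidance moves gaze directly by 0.8 SD, fear does not differ by arm, and gaze tracks fear within arm. Entries are the percentage of trials whose 95% interval for the false indirect effect excludes zero.

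| N | reverse only, no covariates | reverse only, baseline PRPSA and in-session gaze added | guidance moves gaze directly, no covariates |
|---|---|---|---|
| 40 | 2–17 | 1–8 | 22–51 |
| 60 | 4–29 | 1–17 | 38–78 |
| 80 | 5–42 | 2–29 | 54–91 |

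In the middle column in-session gaze differed by arm but was unrelated to post-treatment gaze within arm, so that column does not repeat step 2. With no group effect on fear and no direct effect on gaze, 1–6% of intervals exclude zero without covariates. Conditioning on post-treatment PRPSA (without the other covariates) lowers the rate to at most about 2% (reverse only) and about 5% (last column).

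**4. What the extra models show when mediation is real.** Let guidance move gaze by 0.5 to 0.8 SD, gaze lower post-treatment PRPSA with path p = 0.3 to 0.5, carry-over be 0.85 and gaze stability to 1 week be 0.6. The true indirect effect runs from -0.5 × 0.3 × 12.75 = -1.9 to -0.8 × 0.5 × 12.75 = -5.1 points.
- One-week PRPSA on gaze, conditioned on post-treatment PRPSA: gaze path about 0, although mediation is real.
- Reverse model that omits post-treatment gaze: a false reverse effect equal to p² of the group effect on 1-week gaze, 9% to 25%.
- Reverse model that conditions on post-treatment gaze: the false reverse path returns to about 0.

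**The case against.** The strongest reply is that aim 2 concerns gaze after the intervention, that the outcome most naturally falls a week after the mediator, and that the mechanism wording explains a choice of priors and is not a conclusion. All of that is fair. It gives partial temporal order, but it does not deal with fear already reduced when gaze was recorded.

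Several stronger readings are tempting and not supported:
- A reader might infer that false mediation will appear. Step 3 shows it can. The rate runs from a few percent to most trials, depending on assumptions.
- A reader might take -0.8 to -2.1 points as what the planned model would return. It is not. Step 2 shows that the planned covariate can remove or reverse it, and the priors are not modelled. The 0.85 carry-over has no source in the documents, and the SAP says it could not predict whether gains would rebound or continue.
- A reader might infer that post-treatment PRPSA was completed before the speech task. The protocol lists questionnaires first, but a list does not fix a sequence.
- A reader might infer that gaze was recorded only after treatment. That holds for the chosen mediator. Table 1 also schedules eye tracking at baseline and in both sessions. In-session gaze precedes post-treatment PRPSA, but PRPSA is not collected in the sessions, so using it would not fully settle direction.
- A reader might let the conditioned and reverse models decide whether causal wording is allowed. Step 4 rules this out: a true mechanism complete by the post-treatment visit also gives a null conditioned path.

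**Conclusion.** The concern holds in limited form. The mediator is taken after all treatment and at the same visit as post-treatment PRPSA. The SAP describes neither conditioning on that PRPSA nor a reverse-order check. The planned model therefore cannot separate gaze changing fear from fear changing gaze, and the second can appear as mediation of 1-week PRPSA. That conclusion follows from the documents alone.

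Its size does not. The -0.8 to -2.1 points (9% to 25% of the total) rest on the assumed SD, correlations and carry-over, and on in-session gaze being left out or not differing by arm. With a 0.8 SD arm shift in that covariate the range becomes -0.1 to +2.0 points. The outcome wording needs correcting, though Figure 3 may already show which visit is meant.

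**What to change.** 1. Name 1-week PRPSA as the single aim 2 outcome and make the text agree with Figure 3.
2. Report two models beside the planned one: (a) 1-week PRPSA on group and post-treatment gaze, conditioning on post-treatment PRPSA; (b) 1-week gaze on group and post-treatment PRPSA, conditioning on post-treatment gaze.
3. Describe the planned indirect effect as an association whose direction is not established. Treat a gaze path that survives (a) as supporting evidence for the forward direction. State that a null in (a) is inconclusive, because conditioning also removes true gaze effects already present at post-treatment. Do not use (a) and (b) as a pass/fail rule for causal wording.
4. Do the same for LSAS.

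Table 1 schedules every measurement needed, so no new data collection is required. The cost is revised SAP wording, two further models for each outcome, and a weaker mechanism claim.

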Research Proposal

Efficacy of an Attention Guidance VR Intervention for Social Anxiety Disorder

Study Protocol

Date: 06/18/2020

Identifiers: NCT03683823 Unique Protocol ID: 2018-04-0011

Research Proposal

1. Title

Efficacy of an attention guidance VR intervention for social anxiety disorder

2. Principal Investigator

[name], [name], Psychology
[name], [name], Psychology
[name], [name], Psychology

3. Purpose

Social anxiety disorder (SAD) is a prevalent mental health concern with 12% lifetime prevalence^{1,2}. SAD rarely remits without treatment³ and is associated with significant reduction in quality of life^{4,5}, functional impairment⁶, and significant financial burden⁷. Even following treatment, improvements in symptoms are modest, with meta-analyses of empirically supported treatments indicating only moderate effect sizes^{8,9} and remission rates that are only approximately 30-40%¹⁰.

Attentional processes (i.e. how attention is allocated towards salient information) have been implicated in the maintenance of anxiety disorders, including SAD¹¹. Among individuals with SAD, there is evidence of heightened avoidance of faces (i.e. threat of negative social evaluation)^{12,13-16}. This pattern of avoidance may operate as a maintaining risk factor for SAD¹⁷, and thus a potentially important treatment target.

The primary aims of this study are two-fold. First, we propose to conduct a pilot randomized clinical trial to assess the efficacy of an attentional redirection treatment augmentation strategy for enhancing the outcome of exposure therapy for SAD. Second, we propose to conduct mediational analyses to examine whether the experimental intervention exerts its effects by reducing face avoidance.

4. Procedures

See Table 1 (below) for a summary of the visit measures, and Figure 2 (below) for a diagram of the study design. Completion of the entire study is estimated to take approximately 3 ½ hours.

A. Online Prescreen

Participants will complete brief online questionnaires to assess for social anxiety (LSAS and PRPSA). Participants will be invited based on their scores on the LSAS and PRPSA (see Eligibility criteria below).

We will recruit up to 200 participants in order to enroll 80 participants who meet criteria for the study.

VISIT 1

Baseline Assessment (approximately 45 minutes)

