Informed Consent: Participants will view a brief video about the purpose, risks, and benefits of the study. They will also be informed that participation is voluntary, and that they can withdraw from the study at any point in time. The researcher will then answer any questions the participant might have about the study and the consent form. Participants will indicate

Research Proposal

their willingness to participate by signing a consent form on Qualtrics (see the ‘obtaining informed consent’ section below for more details). Participants will be able to print a copy of the ICD or will be given a copy by a researcher.

Self-report Questionnaires: Participants will then be seated in front of a computer screen and asked to complete a series of questionnaires (see below for a breakdown of the specific measures).

Interview: One of the researchers (a graduate student in clinical psychology) will use selected modules from the SCID-5 (Structured Clinical Interview for DSM-5) to assess the presence of any of the following DSM-5 mental disorders: alcohol or substance use disorders; bipolar disorder; psychosis; and social anxiety disorder. Suicidal risk will be assessed with the Columbia Suicide Severity Rating Scale (C-SSRS).

Behavioral Approach Task: Participants will be fitted with oculus rift headset and then complete a 3-minute speech on an assigned topic, which will be given while watching the video of an audience filmed with 360°-video that is displayed on the oculus rift. This procedure has been previously used in our prior study (IRB # 2016-08-0025).

Figure 1. A researcher wearing the oculus rift VR headset and standing at the podium

Randomization: Following the baseline assessment, if participants are eligible they will be randomized to one of the two intervention conditions (described below).

Intervention – Session 1 (approximately 1 hour)

Intervention Procedures:

Common Intervention Procedures. All participants will complete two intervention (i.e. exposure) sessions within one week. All exposures will be conducted using the VR equipment with videos of an audience, similar to the BAT described above. The intervention will use a standardized protocol. A similar approach has been used by a several studies investigating experimental behavioral intervention strategies for SAD¹⁸⁻²⁰. See below for protocol details:

Research Proposal

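### If the in-session gaze covariate is in the aim 2 group-to-mediator equation, as the SAP's wording implies, the mediated effect can be biased in either direction by an unknown amount

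*SAP*

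**What the plan says.** The protocol (section 3, Purpose) sets the second aim as "mediational analyses to examine whether the experimental intervention exerts its effects by reducing face avoidance". In the SAP (Data Analysis Plan) the mediator is the share of fixations on uninterested, socially threatening audience members at post-treatment. The indirect effect is examined "on the relationship between intervention group and the post-treatment assessment of PRPSA at the 1-week-followup (see Figure 3"). The analysis is repeated for the LSAS.

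The SAP then adds a covariate throughout: "In all models, we included average proportion of fixations to audience members during intervention sessions as a covariate to control for variation in treatment adherence". No exception is made for any equation.

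On timing and content, the protocol (section 4, Procedures) says:
- Randomisation comes before any session: "Following the baseline assessment, if participants are eligible they will be randomized to one of the two intervention conditions".
- Guidance arm, instruction: "They will be told that they should look at and focus on the target audience member for the whole speech".
- Guidance arm, feedback: "between speeches, the researcher will tell participants the percentage of time they were focused on the target face".
- Control arm: participants "will not receive any of the attention guidance components used in the experimental condition".
- Table 1 schedules eye tracking at baseline, in both sessions, at post-treatment and at the 1-week follow-up.

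The SAP also lists integrity checks: group differences in the number of in-session fixations on the audience, and in the proportion on uninterested members afterwards. The sensitivity analyses it describes (Prior Estimates) vary only the priors; none drops the covariate.

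**The concern.** For aim 2, the group-to-mediator path (a-path) should be the effect of assignment on post-treatment gaze. In-session gaze lies between the two in time, and it is what the guidance components are meant to shift. Holding it constant leaves only the part of the group effect that bypasses it.

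The adherence rationale does not fit well. Control participants are given no gaze instruction, so their in-session gaze is not adherence to one. The SAP also treats in-session gaze as something the augmentation should change, since it tests the groups for a difference.

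A second problem is separate. If a personal tendency to look at or away from people drives both gaze measures, conditioning on the first distorts the group comparison on the second, even when none of the effect runs through in-session gaze.

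Mediation is one of two primary aims. The SAP uses this pilot to judge whether a larger trial is worthwhile, although it ties no decision rule to mediation.

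**Working it through.** **The plan's own figure.** The SAP (Power analysis) says a pre-COVID simulation found 60 participants sufficient for both aims. It gives no error rate, SD, effect size or path coefficients, so 60 cannot be reproduced. The argument does not depend on it. No size for the indirect effect is given.

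**Assumed inputs.** G = group, C = in-session gaze, M = post-treatment gaze, Y = PRPSA, U = unmeasured common cause. C and M have within-group SD 1.
- C = G + 0.5U + e (U omitted where there is no common cause)
- M = 0.8(1 - s)G + 0.8sC + hU + e, where s is the share of the group effect running through C
- Y = -0.4M + dC + e

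The true indirect effect is [0.8(1 - s) + 0.8s] x (-0.4) = -0.32 at every s.

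**Step 1: C in both equations.** Within group, C predicts M with slope 0.8s + 0.5h. The adjusted a-path is therefore 0.8 - (0.8s + 0.5h) = 0.8(1 - s) - 0.5h. Multiplying by -0.4:

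| Share s | No common cause | h = 0.3 | h = 0.5 |
|---|---|---|---|
| -50% | -0.48 | not run | not run |
| -25% | -0.40 | not run | not run |
| 0% | -0.32 | -0.26 | -0.22 |
| 25% | -0.24 | -0.18 | -0.14 |
| 50% | -0.16 | -0.10 | -0.06 |
| 75% | -0.08 | -0.02 | +0.02 |
| 100% | 0.00 | +0.06 | infeasible |

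The last cell leaves M no residual variance. A negative share is possible because the instruction concerns one target member, the covariate pools the audience, and the mediator concerns uninterested members. More in-session audience gaze could go with less later gaze at uninterested members.

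**Step 2: C in the outcome equation only.** The a-path is 0.8 and the b-path -0.4, giving -0.32. Least-squares fits to 1,000,000 simulated participants per case stay within 0.01 of this for shares of 0 to 100%, with and without the common cause.

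**Step 3: C in neither equation (no common cause).** If C acts on Y directly, the b-path becomes -0.4 + 0.8sd and the product 0.8(-0.4 + 0.8sd).
- s = 50%, d = -0.2 or -0.4: -0.38 or -0.45.
- s = 100%: -0.45 or -0.58.
- With no true mediator effect the product is 0.64sd: -0.06 or -0.13 (50%), -0.13 or -0.26 (100%). Outcome-equation-only adjustment gives 0.00.

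**Step 4: other coefficients and measurement error.** With a = 0.5 and b = -0.5 (true -0.25), adjusting both equations gave -0.248, -0.187, -0.125, -0.062 and -0.002 at shares of 0 to 100%. If C is measured imperfectly, removal is incomplete: at 100%, reliabilities of 0.9, 0.7 and 0.5 leave -0.025, -0.074 and -0.123.

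**Step 5: small samples.** The table gives the chance that a flat-prior 95% interval for the indirect effect excludes zero (no common cause, d = 0, 1,500 replicates). N = 40 is an assumption; the achieved N is not given.

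| Share | N=60, both | N=60, outcome only | N=40, both | N=40, outcome only |
|---|---|---|---|---|
| 0% | 0.63 | 0.71 | 0.33 | 0.40 |
| 25% | 0.40 | 0.68 | 0.19 | 0.39 |
| 50% | 0.22 | 0.63 | 0.10 | 0.35 |
| 75% | 0.06 | 0.56 | 0.03 | 0.27 |
| 100% | 0.02 | 0.35 | 0.01 | 0.19 |

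The SAP gives no numerical priors for gaze, so its informative priors could not be used here. They could pull the adjusted a-path back towards the prior.

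**The case against.** The best reply is that *all models* may not be meant literally. Adjusting the check on in-session fixation counts for in-session fixation proportion would largely defeat that check, so the phrase may cover only the PRPSA and LSAS outcome models. No equations are printed; the layout is left to Figure 3 and posted syntax, neither of which is in the text supplied. This stands as a limit: with the covariate in the outcome equation only, the bias does not arise. But the sentence is written as a rule without exceptions, and the plain reading includes the a-path.

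Second, the check on post-treatment gaze, if unadjusted, would show the total group-to-mediator effect. That is a partial safeguard, but the text does not say it is unadjusted, and it does not restore the indirect effect.

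Third, the share is unknown and may be zero. The in-session check uses counts while the covariate is a proportion, so the documents do not show that assignment moves the covariate. This also stands.

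Three stronger inferences are tempting and not supported:
- *The mechanism must be understated.* The three gaze quantities differ, so overstatement and a sign change are also possible.
- *Aim 1 is biased too.* A person-level covariate entered additively leaves the group-by-assessment interaction unchanged with complete data and flat priors.
- *The covariate should go altogether.* Step 3 shows that this can inflate the indirect effect or create a spurious one.

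**Conclusion.** The point holds conditionally. Followed as written, the SAP's aim 2 a-path is not the effect of assignment on post-treatment gaze, and the product of paths is not the mediated effect that the protocol describes. Against an assumed true value of -0.32, the estimates run from -0.48 to +0.06 over the cases shown. They equal the true value only when nothing runs through in-session gaze and no common cause exists.

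This rests on the covariate being in the group-to-mediator equation, on linear models without interactions, and on assumed coefficients. Recovering the effect by outcome-equation adjustment also requires no unmeasured common cause of post-treatment gaze and PRPSA. The documents establish the specification problem, not its size or direction in this trial. It should be fixed; confidence is medium because the equations are not visible.

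**What to change.** - Write out the aim 2 equations for PRPSA and LSAS, including which assessment supplies the outcome (the SAP sentence names both post-treatment and 1 week). If the covariate was already only in the outcome equation, saying so settles the bias.
- Otherwise omit in-session gaze from the group-to-mediator equation, the total-effect model and the integrity check on post-treatment gaze.
- Keep it in the mediator-to-outcome equation, where it may be a confounder, and report a version without it as a sensitivity analysis.
- The SAP describes completed analyses, so label the change post hoc and show the fully adjusted results beside the new ones.

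The cost is a few sentences and a re-run of existing code, with no new data. Three downsides should be stated:
- Changing a main specification after analysis adds flexibility, and the new result may disagree with the old.
- Precision falls when the two gaze measures are closely related. At N = 60 the SD of the estimate rises from 0.15 (0% share) to 0.22 (100%).
- Indirect plus direct will no longer equal total, because the path from group through in-session gaze to the outcome that bypasses the mediator is in neither term. In the assumed model that remainder is 1 x d, or -0.20 and -0.40 for d = -0.2 and -0.4. Report it separately.

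No change to aim 1 is needed.
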